8.4.2 DEFINITION OF SERIOUS ADVERSE EVENTS

For study purposes, a serious adverse event (SAE) is any AE that results in death, is life-threatening, or places the participant at immediate risk of death from the event as it occurred; requires or prolongs hospitalization, causes persistent or significant disability or incapacity, or results in congenital anomalies or birth defects. Additionally, any other important medical event may be considered an SAE if it is judged by the investigators to jeopardize the safety of a participant or to require medical or surgical intervention to prevent one of the above outcomes listed in this SAE definition.

8.4.3 CLASSIFICATION OF AN ADVERSE EVENT

8.4.3.1 SEVERITY OF EVENT

Using the Common Terminology Criteria for Adverse Events (CTCAE) system, all adverse events detected in this study will be graded in severity using the 5-point CTCAE scale. According to this scale, AEs are considered grade 1 if they represent only mild symptoms or asymptomatic laboratory findings; grade 2 if they cause moderate symptoms that interfere with instrumental activities of daily living (shopping, transportation, household tasks); grade 3 if they are serious or disabling events or result in hospitalization or prolongation of hospitalization without being directly life-threatening; grade 4 if they are life-threatening events in which the participant is at risk of death at the time of the event if immediate intervention is not undertaken; or grade 5 if they are

fatal adverse events. By definition, a “serious adverse event” is an adverse event that is CTCAE severity grade 3 or higher.

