8.4.4 TIME PERIOD AND FREQUENCY FOR EVENT ASSESSMENT AND FOLLOW-UP

New AEs or SAEs will be considered reportable any time after the Baseline Clinic Visit (which is the first scheduled visit involving in-person assessments) until 7 days (for non-serious AEs) or 30 days (for SAEs) after the last day of study participation.

Clinical coordinators at each site will proactively assess for adverse events by asking participants about negative changes they have experienced in their health at scheduled follow-up study visits and telephone assessments starting with the 2-Week Telephone Call. Coordinators will not prompt participants to provide information about specific types of adverse events, but instead will encourage participants to volunteer information by asking a standardized, open-ended question, “Have there been any changes in your health since your last visit?” Any negative changes in health reported in response to this question will then be recorded on standardized forms.

Participants will also be given telephone numbers at baseline to call study staff before the scheduled 2-week telephone call or between scheduled study visits or calls to report negative changes in their health. If reported, these changes will be recorded on standardized adverse event forms.

Medical or psychiatric conditions that are present at the time that participants are screened will be considered to reflect participants' baseline status and will not be reported as adverse events. However, if the study participant's condition deteriorates at any time during the study, this deterioration will be recorded as an AE even if it is related to a pre-existing condition.

Adverse events will be characterized by clinical coordinators at each clinical site in collaboration with the Site Principal Investigator (Site PI) or other investigators if appropriate. The clinical coordinator in conjunction with the Site PI will document events on standardized adverse event forms. The Site PI will review information about individual AEs collected by clinical coordinators twice monthly to guide determinations about the relationship to study interventions, expectedness, and severity.

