8.4.5 ADVERSE EVENT REPORTING

Non-serious adverse events detected during the course of the trial will be reported to NCCIH on an annual basis by way of inclusion in the annual report and in the semi-annual AE summary which will be provided to the DSM and the NCCIH. The DSM Report will confirm that all AEs have been reviewed.

Non-serious adverse events will not automatically be reported to the UCSF IRB, but the Principal Investigator may report or consult the UCSF IRB for input on the handling of non-serious AEs if they may still pose a substantial risk of harm to a participant or are potentially associated with study interventions or procedures.

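### Sections 8.4.2 and 8.4.3.1 give two non-equivalent definitions of a serious adverse event, and they part on disabling events that are neither hospitalized nor persistent

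*Combined protocol and SAP*

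**What the plan says.** Section 8.4.2 sets the definition for study purposes. An adverse event is serious if it is fatal or life-threatening, or if it "requires or prolongs hospitalization, causes persistent or significant disability or incapacity, or results in congenital anomalies or birth defects". A discretionary clause follows: "any other important medical event may be considered an SAE if it is judged by the investigators to jeopardize the safety of a participant". The same clause covers an event judged to need intervention to prevent a listed outcome. That clause has no grade threshold.

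Section 8.4.3.1 grades severity on the five-point CTCAE scale, described in the protocol's own words. An event is "grade 2 if they cause moderate symptoms that interfere with instrumental activities of daily living", and "grade 3 if they are serious or disabling events or result in hospitalization or prolongation of hospitalization without being directly life-threatening". Grade 4 is life-threatening and grade 5 is fatal. The section ends by stating that, by definition, a serious adverse event "is an adverse event that is CTCAE severity grade 3 or higher".

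Other rules then depend on seriousness. Section 8.4.4 makes events reportable "until 7 days (for non-serious AEs) or 30 days (for SAEs) after the last day of study participation". Section 8.4.5 says "Non-serious adverse events detected during the course of the trial will be reported to NCCIH on an annual basis" (and in a semi-annual summary to the monitor and NCCIH), and that "Non-serious adverse events will not automatically be reported to the UCSF IRB". Sections 8.4.6 and 8.5.2 set faster clocks for SAEs, and Section 9.4.11 lists only SAEs individually.

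**The concern.** Seriousness and severity are different attributes. One is about outcome or required action, the other about intensity. Section 8.4.2 treats seriousness in the first way, and Section 8.4.3.1 turns it into a grade cut-off. Both are worded as the definition, and neither gives way to the other.

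If the two rules selected the same events, this would be untidy but harmless. If they do not, a coordinator and Site PI who follow one section can classify an event differently from colleagues at another site who follow the other. The reporting route, the capture window and the listing would then differ for the same clinical event.

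The kind of event involved is plausible in this trial. Section 8.2.1 names strain and musculoskeletal injury as risks in both arms. Section 8.4.4 counts deterioration of a pre-existing condition as an adverse event, which would take in a pelvic pain flare.

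**Working it through.** There is no figure in the plan to reproduce. The check compares the two definitions and then traces what depends on them.

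**Step 1. Compare the definitions.**

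| Event | Section 8.4.2 | Section 8.4.3.1 | Agree? |
|---|---|---|---|
| Fatal | Serious | Grade 5, serious | Yes |
| Life-threatening | Serious | Grade 4, serious | Yes |
| Hospitalization, new or prolonged | Serious | Grade 3, serious | Yes |
| Disabling and persistent | Serious | Grade 3, serious | Yes |
| Disabling, not persistent, no hospitalization | Serious only if the disability is judged significant or the event is judged important | Grade 3, serious automatically | Not necessarily |
| Severe symptoms, not disabling, no hospitalization | Serious only if judged important | Grade 3 only if already called serious | No independent test |

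The fifth row is the main discordant set. Grade 3 needs only that the event be disabling, without qualification. Section 8.4.2 requires the disability to be persistent or significant, or else a judgment under a clause that permits a serious classification without requiring it.

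The sixth row shows the circularity. Grade 3 is described partly by the word *serious*, and *serious* is then defined as grade 3 or higher.

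**Step 2. Trace what follows for an event in the fifth row.**

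| Rule | If serious | If not serious | Sections |
|---|---|---|---|
| Reporting, if unexpected and related | 7 days | Annual report and semi-annual summary | 8.4.6, 8.4.5 |
| Reporting to NCCIH, if anticipated or unrelated | Semi-annual | Annual report and semi-annual summary | 8.4.6, 8.4.5 |
| If it is an unanticipated problem | 7 days | 14 days | 8.5.2 |
| Capture after last day of participation | 30 days | 7 days | 8.4.4 |
| Documentation | SAE form, and contact between visits | AE form, updated at scheduled contacts | 8.4.4 |
| Individual listing | Yes | No | 9.4.11 |

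**Step 3. Limit the effect.**

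- The 3-day clock in Section 8.4.6 covers only fatal or life-threatening events. These are serious under both sections, so that clock does not change.
- An unexpected, related event that also meets the third criterion of Section 8.5.1 (greater risk than previously known) is an unanticipated problem. For it, the slow route is 14 days rather than the periodic summary.
- The capture windows differ by 30 − 7 = 23 days. In those 23 days, the definition used decides whether a new event is reportable at all.

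**The case against.** The strongest case on the other side has four parts.

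**The overlap is wide.** The protocol's grade 3 text already includes hospitalization, and the disability criterion in 8.4.2 is met if disability is persistent *or* significant. Being short-lived defeats only the first, and the important-medical-event clause is a further route. This stands, and it narrows the discordant set. It does not close it, because one section classifies automatically and the other leaves a judgment.

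**The gap does not clearly run both ways.** A reader might infer that low-grade important medical events, or congenital anomalies, are serious under 8.4.2 but not under 8.4.3.1. The documents support this only weakly. An event judged serious under 8.4.2 can be read into grade 3, whose description includes serious events. Pregnancy, the setting for a congenital anomaly, has its own reporting rule in Section 8.4.9. The point does not rest on this direction.

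**The consequences are modest.** Strain and musculoskeletal injury are listed risks, and a pain flare belongs to the condition under study, so many such events would be expected under Section 8.4.3.3. NCCIH would then hear of them on nearly the same timing either way. This stands in part. The same section makes an event unexpected if its severity does not fit the protocol information, so a disabling strain could still reach the 7-day route. The capture window, SAE form and listing differ whatever the expectedness.

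**Staff could apply both.** Neither section says *only*, so treating an event as serious if it meets either test would be workable. The Data and Safety Monitoring Plan cited in Section 10.1.6 may also name a governing definition. It is not among the documents and cannot be checked. It would therefore be too strong to say that the sections cannot be operated together. But the either-test rule is not written down, and a definition held elsewhere would leave the conflict in the protocol.

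**Conclusion.** The concern holds. The protocol contains two definitions of an SAE that are not equivalent, with no rule of precedence. The disagreement is confined mainly to disabling, non-hospitalized events that are not persistent. The circular grade 3 description adds uncertainty for severe events that neither disable nor hospitalize.

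For an affected event, the size is the set of contrasts shown in the working: 7 days against annual or semi-annual reporting if unexpected and related, 7 against 14 days if an unanticipated problem, and 30 against 7 days of capture, together with forms, follow-up and listing.

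Two stronger readings are tempting and not supported:

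- A reader might infer that the SAE rate would shift by a stated amount. One event in 36 women is 1/36 = 2.8% and two are 2/36 = 5.6%, but this is only what each event contributes. The documents give no expected event rates, so the number of affected events cannot be estimated.
- A reader might infer that a published comparison of SAEs by arm is at risk. Section 9.4.7 plans no formal between-group safety analysis and promises aggregate adverse event information. Section 10.1.11 promises important adverse events. Neither names an SAE count by arm, and the composite feasibility outcome in Section 9.4.5 does not use one.

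The conclusion assumes that both sections are in force as written. It is an internal inconsistency in a core safety rule, and it should be corrected.

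**What to change.** Reconcile Sections 8.4.2 and 8.4.3.1 to a single governing definition of an SAE. One way is to remove the sentence in 8.4.3.1 that equates seriousness with grade 3 or higher and point to 8.4.2 instead. Whichever definition the investigators adopt, the protocol should state it once, and the Data and Safety Monitoring Plan should be checked against it.

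Record CTCAE grade as a severity field separate from seriousness, and remove the word *serious* from the grade 3 description so that the grade can be assigned on its own terms.

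The cost is one or two sentences in the protocol and a check that the adverse event form holds seriousness and severity separately. No new data are collected.

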8.4.3.2 RELATIONSHIP TO STUDY INTERVENTION

All AEs will also be categorized according to the likelihood that they are related to the therapeutic study interventions. Specifically, AEs will be labeled as unrelated, unlikely related, possibly related, probably related, or definitely related, based on the opinion of the Site PI:

- *Unrelated*: the time course between administration of the study intervention and occurrence or worsening of the AE rules out a causal relationship, and/or another cause is confirmed and no indication of involvement of the study intervention in the occurrence or worsening of the AE exists.
- *Unlikely related*: the time course between administration of the study intervention and occurrence or worsening of the AE makes a causal relationship unlikely, and/or; the known effects of the study intervention provide no indication of involvement in the AE and another cause adequately explaining the AE is known, and/or; a plausible causal chain may be deduced from the known effects of the study intervention, but another cause is much more probable, and/or; another cause is confirmed and involvement of the study intervention in the AE is unlikely.
- *Possibly related*: a plausible causal chain may be deduced from the nature of the study intervention, but another cause just as likely to be involved is also known, or; although the nature of the intervention does not create a strong expectation of involvement in the AE, involvement of the intervention is still possible, and no other cause gives adequate explanation.
- *Probably related*: The nature of intervention indicates that it probably caused the AE, and/or; the course of the AE after stopping study intervention improved and, if applicable, worsened after re-challenge, and/or; a specific test suggests the involvement of the study intervention, although another cause cannot be ruled out.
- *Definitely related*: The biological properties of the study intervention are known to cause the AE, and/or; the AE improves after stopping study intervention and, if applicable, worsens after re-challenge, and/or; a specific test indicates the involvement of the study intervention, and no indication of other causes exists.

8.4.3.3 EXPECTEDNESS

Adverse events will be assessed as to whether they were expected to occur or unexpected (i.e., not anticipated based on current knowledge found in the protocol or known information about the study intervention). Categories are:

- 1) *Unexpected* – the nature or severity of the event is not consistent with information about the condition under study or intervention in the protocol, consent form, or product brochure; or
- 2) *Expected* – the event is known to be associated with the intervention or condition under study.

8.4.4 TIME PERIOD AND FREQUENCY FOR EVENT ASSESSMENT AND FOLLOW-UP

New AEs or SAEs will be considered reportable any time after the Baseline Clinic Visit (which is the first scheduled visit involving in-person assessments) until 7 days (for non-serious AEs) or 30 days (for SAEs) after the last day of study participation.

Clinical coordinators at each site will proactively assess for adverse events by asking participants about negative changes they have experienced in their health at scheduled follow-up study visits and telephone assessments starting with the 2-Week Telephone Call. Coordinators will not prompt participants to provide information about specific types of adverse events, but instead will encourage participants to volunteer information by asking a standardized, open-ended question, “Have there been any changes in your health since your last visit?” Any negative changes in health reported in response to this question will then be recorded on standardized forms.

Participants will also be given telephone numbers at baseline to call study staff before the scheduled 2-week telephone call or between scheduled study visits or calls to report negative changes in their health. If reported, these changes will be recorded on standardized adverse event forms.

Medical or psychiatric conditions that are present at the time that participants are screened will be considered to reflect participants' baseline status and will not be reported as adverse events. However, if the study participant's condition deteriorates at any time during the study, this deterioration will be recorded as an AE even if it is related to a pre-existing condition.

Adverse events will be characterized by clinical coordinators at each clinical site in collaboration with the Site Principal Investigator (Site PI) or other investigators if appropriate. The clinical coordinator in conjunction with the Site PI will document events on standardized adverse event forms. The Site PI will review information about individual AEs collected by clinical coordinators twice monthly to guide determinations about the relationship to study interventions, expectedness, and severity.

Adverse event forms will indicate the severity of the event, the likelihood of relationship to study interventions, and the expectedness of the event. Adverse event forms will also note the date of onset of the adverse event, record whether the event has resolved or is continuing at the time of assessment, record the date of resolution, and note any important study actions taken in response to the event. For SAEs, standardized SAE forms will also record the nature of the event, the outcome of the event to date, whether

the event resolved or continues, and any medications or other treatments provided in response to the SAE.

Any detected AEs and SAEs will be followed until resolved or considered stable. At each scheduled follow-up contact after the initial discovery of an AE or SAE, clinical coordinators will assess whether the AE or SAE is continuing or has resolved, and will update information about event status on the AE or SAE form, as appropriate.

For SAEs, coordinators will also make more active attempts to communicate with the participant in between scheduled study visits (with the participant's permission) to monitor the resolution of SAEs.

8.4.5 ADVERSE EVENT REPORTING

Non-serious adverse events detected during the course of the trial will be reported to NCCIH on an annual basis by way of inclusion in the annual report and in the semi-annual AE summary which will be provided to the DSM and the NCCIH. The DSM Report will confirm that all AEs have been reviewed.

Non-serious adverse events will not automatically be reported to the UCSF IRB, but the Principal Investigator may report or consult the UCSF IRB for input on the handling of non-serious AEs if they may still pose a substantial risk of harm to a participant or are potentially associated with study interventions or procedures.

8.4.6 SERIOUS ADVERSE EVENT REPORTING

SAEs that are unanticipated, serious, and possibly related to the study intervention will be reported to the Independent DSM/MSO, IRB, and NCCIH in accordance with requirements:

- Unexpected fatal or life-threatening SAEs related to the intervention will be reported to the NCCIH Program Officer and Independent DSM/MSO within 3 days of the investigator becoming aware of the event. Other serious and unexpected AEs related to the intervention will be reported within 7 days.
- Anticipated or unrelated SAEs will be handled in a less urgent manner but will be reported to the Independent DSM/MSO, IRB, and other oversight organizations in accordance with their requirements and will be reported to NCCIH on a semi-annual basis.

8.4.7 REPORTING EVENTS TO PARTICIPANTS

The investigative team may inform participants about other individual or aggregate level AEs or SAEs detected in the course of the study if these events have important implications for the risks associated with study participation. The decision to inform participants about other AEs or SAEs will be made by the investigative team with input from the IRB, the DSM, and other regulatory bodies as necessary.

If information about AEs or SAEs is shared with participants who were not directly involved in the events, then the study team will share information in such a way as to protect the confidentiality and privacy of the individuals involved.

8.4.8 EVENTS OF SPECIAL INTEREST

For this study, special procedures have been developed to monitor and follow-up participants' scores on selected questionnaires assessing depression or anxiety symptoms or on questionnaires assessing Post-Traumatic Stress Disorder (PTSD) symptoms. Scores will be reviewed on an ongoing basis to identify participants with elevated scores that may indicate increased risk of at least moderate depression or anxiety or PTSD.

Procedures for reviewing and notifying participants about potentially concerning scores on these measures are described in detail in the Data & Safety Monitoring Plan (DSMP). For score elevations indicating moderately increased risk of depression or anxiety, the study team will arrange for the participant to receive a standardized letter indicating the score and the normal score range, along with a recommendation that participants seek further evaluation or treatment from a health care provider and a list of mental health resources in the area. For score elevations indicating severely increased risk of depression or anxiety or indicating clinically significant PTSD symptoms, a study clinician will additionally attempt to contact the participant by telephone.

8.4.9 REPORTING OF PREGNANCY

Screening procedures have been designed to exclude women who are pregnant or planning to become pregnant during the study period. If a participant becomes pregnant after enrollment in the study, this event will be reported to the DSMs, IRB, and NCCIH in the same time frames and using the same procedures as a serious and unexpected SAE, even if pregnancy is not accompanied by other conditions of an SAE.

Any participant discovered to be pregnant after study enrollment will discontinue participation in the study interventions, but will be permitted to continue contributing follow-up data. If permitted by the participant, study staff will continue to follow the participant until the resolution of the pregnancy.

